8.5.3 Pharmacokinetics Procedure and Assessment

Blood samples for MEN1309, tAb, DM4 and its metabolite S-methyl-DM4 serum concentration measurements will be taken before (pre-dose) and immediately after the end of each IV infusion during all cycles for each cohort. If any interruption occurs during MEN1309 infusion at any cycle, an additional blood sampling for PK will be taken at the time of each infusion interruption and just before each infusion resumption.

Furthermore, blood sampling for PK are obtained at 1, 2, 4, 6, 8, 10, 12, 16, 24, 36, 48, and 72 hours after the end of the infusion of Cycle 1 and Cycle 2 (see §2.4). For Cycle 2, PK blood sampling at 10, 12 and 16 hours after the end of infusion is informative but not mandatory.

For Cycles 3+, PK blood samples will be taken only before the start of infusion and immediately after the end of infusion, as well as in conjunction with any safety blood samples taken up to 72 hours after the end of infusion.

For dose levels higher or equal to 0.8 mg/kg, in case additional sampling for safety testing is required (e.g., between study visits), an additional blood sample for PK will also be taken at the same time. Moreover, only for dose levels higher or equal to 0.8 mg/kg, PK blood samples will be taken at Visits 2 and 3 of each cycle in conjunction with safety blood samples (see § 2.4).

The following pharmacokinetic parameters will be determined from the individual serum concentration-time curve for MEN1309, tAb, DM4 and its metabolite S-methyl-DM4, when applicable, using non-compartmental methods with Phoenix™ WinNonlin® software, version 6.4 or higher (Pharsight Corp., Mountain View, California).

| | |
|---------------------|--|
| C_{\max} | Maximum observed serum concentration. |
| t_{\max} | Time to C_{\max} . |
| C_{last} | Last quantifiable serum concentration value. |
| t_{last} | Time to C_{last} . |
| C_{trough} | Pre-dose serum concentration. |
| k_e | Apparent terminal elimination rate constant, estimated by log-linear regression analysis on serum concentrations visually assessed to be on the terminal log-linear phase. |
| $t_{1/2}$ | The terminal serum half-life, calculated according to the following equation: |
| | $t_{1/2} = \frac{0.693}{k_e}$ |
| $AUC_{(0-t)}$ | Area under the serum concentration-time curves from time zero (pre-dose) to the time of the last quantifiable concentration, calculated by means of the linear-log trapezoidal method. |
| $AUC_{(0-\infty)}$ | Area under the serum concentration-time curve from time zero to infinity, calculated according to the following equation: |
| | $AUC_{(0-\infty)} = AUC_{(0-t)} + \frac{C_{\text{last}}}{k_e}$ |
| $\%AUC_{\text{ex}}$ | The percentage of $AUC_{(0-\infty)}$ obtained by extrapolation calculated as follows: |

$$AUC_{\text{ex}}(\%) = \frac{AUC_{(0-\infty)} - AUC_{(0-t)}}{AUC_{(0-\infty)}} * 100$$

| | |
|---------------------|--|
| CL | Systemic clearance, calculated according to the following equation: |
| | $CL = \frac{Dose}{AUC_{(0-\infty)}}$ |
| V_{ss} | Volume of distribution at steady state, calculated according to the following equation: |
| | $V_{ss} = CL * MRT$ |
| V_d | Volume of distribution based on the terminal phase, calculated according to the following equation: |
| | $V_d = \frac{Dose}{k_e * AUC_{(0-\infty)}}$ |
| $AUMC_{(0-\infty)}$ | The area under the first moment curve from zero to infinity calculated using the equation: |
| | $AUMC_{(0-\infty)} = \sum_{i=0}^{n-1} \frac{t_{i+1} - t_i}{2} (C_i t_i + C_{i+1} t_{i+1}) + \frac{t * Ct}{k_e} + \frac{Ct}{k_e^2} + \frac{t \cdot C_t}{\tau} + \frac{C_t}{\tau^2}$ |
| MRT | Mean residence time was calculated as: |
| | $MRT = AUMC_{(0-\infty)} / AUC_{(0-\infty)}$ |
| Ro | Accumulation ratio following 2 consecutive infusions calculated as: |
| | $Ro = AUC_{(0-t)}^{2nd} / AUC_{(0-t)}^{1st}$ |

PK parameters will be calculated after the first and second infusion of each dose cohort. C_{max} and C_{trough} will also be obtained after each administration of MEN1309. Actual PK sampling times will be used in the derivation of PK parameters. Alternatively, it is also acceptable to consider the planned sampling times if they do not deviate by more than 5% from the actual. Planned sampling times may be used as a replacement for unknown or missing actual times.

The calculation of the parameters listed above and others will depend upon the results of the drug concentration assay and the duration of drug infusions.

For the calculation of individual PK parameters, values Below the Lower Limit Of Quantification (BLOQ) will be handled as follows:

1. BLOQ values located before the t_{max} of their affiliating curve will be transformed to zero.
2. If a BLOQ value located after the t_{max} falls between 2 quantifiable concentrations, it will be omitted from the PK analysis.
3. If, within a dosing interval, 2 or more BLOQ values occur in succession after quantifiable concentrations, the profile will be deemed to have terminated at the first BLOQ value and

94 of 126

any subsequent concentrations in that dosing interval will be omitted from the non-compartmental analysis.

4. In some circumstances, when a PK rationale exists, BLOQ values may be set to some other values, e.g., half of the Lower Limit of Quantification (LLOQ).

Concentrations reported as >LLOQ at time zero, when the patient has not previously been dosed, will be set to zero.

Exploratory PK/PD analyses may be carried out in order to investigate the relationship between drug exposure and clinical activity of the aforementioned analytes. Methods for these analyses will be described in the Data Analysis Plan included in the Statistical Analysis Plan (SAP).

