6.2.2.3 Toxokinetics (TK)

6.2.2.3.1 *Exploratory single dose intravenous toxicity study of MEN1309 in cynomolgus monkeys was performed*

The TK of the ADC MEN1309 following a single dose intravenous infusion was investigated in 2 cynomolgus monkeys (1 male and 1 female) at 3 different escalating doses (1, 3, and 5 mg/kg). An observation period of 3 weeks was considered between the different administrations. No relevant gender-related differences were observed, and no relevant differences were observed between the concentrations of MEN1309 and those of the Total Antibody.

Finally, a 3-week interval between doses was sufficient to allow a complete clearance of the drug.

6.2.2.3.2 *Toxicokinetics of MEN 1309 following single and repeated administrations in cynomolgus monkeys*

Forty cynomolgus monkeys were randomly sorted in 4 treatment groups; each group, comprising 5 males and 5 females, was intravenously treated by 1 hour infusion for 3 times every 3 weeks with placebo, 0.1, 0.3, and 1 mg/kg of MEN1309, respectively.

The pharmacokinetics were non-linear, as a consequence dose-dependent terminal half-life and clearance were observed. Furthermore, with respect to conventional IgG, shorter terminal half-life and more extensive clearance were found. This evidence is in keeping with a possible TMDD to be mainly ascribed to the expression of the target antigen CD205 on some leukocyte populations. A reduced receptor-mediated ADC uptake in leukocytes could also be responsible for the long-lasting pharmacokinetic profiles observed in some animals.

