8.4.4 MEN1309 Intravenous infusion

Intravenous infusion of MEN1309 lasts 3 hours; however it can be interrupted or slowed to be completed within 6 hours upon Investigator's judgement in case the patient develops infusion-related grade ≥ 2 AEs (CTCAE v. 4.03 definition) and not meeting any treatment discontinuation criteria (see §8.2.3). In case of interruption, the infusion may be resumed when symptoms abate; however, the study drug infusion solution shall be used within 24 hours. It is important that the time when the infusion starts and ends is duly recorded together with the total volume administered over each start/end infusion period.

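### Protocol 8.5.3 defines MRT and Vss without an infusion term, which under linear PK overstates MRT by 1.5 h and Vss by CL × 1.5 h for a 3 h infusion (minor)

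*Protocol*

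**What the plan says.** Protocol 8.5.3 assigns the PK parameters to non-compartmental analysis in named software and then prints a formula for most of them.

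- AUC(0-t) runs "from time zero (pre-dose) to the time of the last quantifiable concentration, calculated by means of the linear-log trapezoidal method". The infusion period therefore lies inside the area.
- AUMC is introduced with "The area under the first moment curve from zero to infinity calculated using the equation" and printed as a linear trapezoid sum plus tail terms.
- MRT follows "Mean residence time was calculated as" and is AUMC(0-∞)/AUC(0-∞).
- Vss follows "Volume of distribution at steady state, calculated according to the following equation" and is CL × MRT, with CL = Dose/AUC(0-∞).

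None of these formulas contains the infusion duration. The only text in the section that links the calculation to it is a general remark that the parameters "will depend upon the results of the drug concentration assay and the duration of drug infusions".

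On dosing, the synopsis and Protocol 8.4.4 give a 3-hour infusion, and 8.4.4 adds that "it can be interrupted or slowed to be completed within 6 hours" if the patient has certain infusion-related events. The same section requires that "the time when the infusion starts and ends is duly recorded together with the total volume administered over each start/end infusion period".

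SAP 5.1.1.5 lists MRT and Vss among the PK endpoints without formulas, so Protocol 8.5.3 is the only written definition.

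**The concern.** The ratio AUMC/AUC is the mean residence time only when the whole dose enters at time zero. After an infusion it also contains the average time that drug molecules waited to enter the circulation. Read literally, 8.5.3 folds that waiting time into MRT and, through CL × MRT, into Vss. The error goes in one direction. It would also differ between patients if some infusions are slowed or interrupted, because the waiting time differs.

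At stake are two named PK endpoints under a secondary objective. CL, AUC, Cmax, half-life and Vd do not use MRT and are unaffected.

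**Working it through.** The documents state no MRT or Vss value, so there is no figure of the plan to reproduce. The check derives the size of the missing term.

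**Inputs.** Infusion length T = 3 h (synopsis), up to 6 h (Protocol 8.4.4). Monkey half-life 15 to 31 h and CL 1.5 to 2.7 mL/h/kg (Protocol 6.2.2.2), used only for scale. Monkey rows of Table 1 (Protocol 6.2.5): 1 mg/kg, Cmax 23.61 µg/mL, AUC 438.5 µg·h/mL; 0.3 mg/kg, 6.45 and 44.2; both over 1 h. Assumptions: one-compartment profiles, with the short half-life paired with the high CL.

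**1. Identity under linear PK.** The infusion curve is the bolus curve convolved with the input, so

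AUMC/AUC = MRT + mean input time.

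For a constant rate the mean input time is T/2: 3/2 = 1.5 h, or 6/2 = 3 h. Numerical integration of a one-compartment model gave excesses of 1.500 h and 3.000 h. An illustrative two-compartment model (CL 2.4 mL/h/kg, T = 3 h) gave MRT 45.94 against 44.44 h and Vss 110.27 against 106.67 mL/kg, a difference of 3.60 = 2.4 × 1.5.

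**2. Size for a 3 h infusion.** True MRT = half-life/ln 2.

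| Half-life, CL | True MRT | As printed | Excess | Vss excess |
|---|---|---|---|---|
| 15 h, 2.7 mL/h/kg | 21.64 h | 23.14 h | 1.5/21.64 = 6.9% | 2.7 × 1.5 = 4.05 mL/kg |
| 31 h, 1.5 mL/h/kg | 44.72 h | 46.22 h | 1.5/44.72 = 3.4% | 1.5 × 1.5 = 2.25 mL/kg |

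A constant 6 h infusion doubles the excess (13.9% and 6.7%; 8.1 and 4.5 mL/kg). Protocol 6.3 reports no infusion-related reactions up to 1.60 mg/kg, so that case was hypothetical when the protocol was written.

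**3. Interrupted infusions.** The term is then the dose-weighted mean of the period midpoints, not T/2. Two examples, both finished at 6 h (T/2 = 3 h):

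- One third of the dose in 0–1 h and two thirds in 4–6 h: 1/3 × 0.5 + 2/3 × 5 = 3.50 h.
- Two thirds in 0–2 h and one third in 5–6 h: 2/3 × 1 + 1/3 × 5.5 = 2.50 h.

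**4. Non-linear PK.** Protocol 6.2.2.3 says of the monkey data: "The pharmacokinetics were non-linear, as a consequence dose-dependent terminal half-life and clearance were observed". I used the model dC/dt = R/V − Vm·C/(Km + C) − k·C with three parameter sets that reproduce the two monkey rows (Cmax within 2.5%, AUC within 0.3%):

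| V (mL/kg) | Vm (µg/mL/h) | Km (µg/mL) | k (/h) |
|---|---|---|---|
| 42.17 | 0.496 | 0.01 | 0.0087 |
| 42.26 | 0.605 | 0.52 | 0.0029 |
| 42.27 | 0.646 | 0.71 | 0.001 |

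At 0.3 to 1 mg/kg, AUMC/AUC for a 3 h infusion exceeds the bolus value by 1.07 to 1.20 h. Subtracting 1.5 h would over-correct by 1.5 − 1.20 = 0.30 h to 1.5 − 1.07 = 0.43 h, which is less than the uncorrected error. At 3 to 5 mg/kg the same fits imply CL of 0.51 to 1.05 mL/h/kg, against 1.5 to 2.7 reported at those doses in 6.2.2.2, so I make no claim there.

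**5. AUMC rule (secondary).** On the scheduled sampling times after a 3 h infusion, with the tau terms in the AUMC line left out, total excess over true MRT is:

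| Half-life, last sample | Linear AUMC | Linear-log AUMC | Due to linear sum |
|---|---|---|---|
| 15 h, 72 h post-infusion | 1.64 h | 1.60 h | +0.04 h |
| 31 h, 72 h post-infusion | 1.36 h | 1.55 h | −0.19 h |
| 15 h, Day 8 | 4.06 h | 1.60 h | +2.46 h |
| 31 h, Day 8 | 2.65 h | 1.55 h | +1.10 h |
| 31 h, Day 15 | 5.71 h | 1.55 h | +4.16 h |

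The 4.06 h row needs quantification at 0.049% of Cmax and the 5.71 h row at about 0.06%, so both depend on the assay's LLOQ. Day 8 and Day 15 samples are taken only at 0.80 mg/kg and above.

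**The case against.** The strongest reply is that 8.5.3 already makes the calculation depend on infusion duration and hands it to standard software, so a correction may be applied in practice. This stands to a degree: a reader might infer that the reported MRT and Vss will be wrong, and the documents do not support that, because the software settings are not stated. But the remark covers all the parameters and gives no rule. If the software does correct, its output will not match the printed formulas. The wording needs changing either way.

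Second, the 1.5 h is exact only under linear PK, and the protocol calls the drug's PK in monkeys non-linear. This also stands. The figure is a guide to size; in the dose range where the fits agree with the monkey data the excess is somewhat smaller, in the same direction.

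Third, the effect is small and nothing is decided on it. That is correct and sets the severity.

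Two larger readings are tempting. One is to invert the predicted human row of Table 1 for a much larger relative bias at 0.05 mg/kg. That assumes a one-compartment structure which 6.2.5 does not state, for a single predicted row at a dose level with one patient under accelerated titration. The other is to attribute the totals above 2 h in step 5 to the missing infusion term. They come mainly from the linear AUMC sum over long gaps, and rest on an equation line whose tau terms may be a text-extraction fault. No error is claimed for those terms.

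**Conclusion.** The concern holds as a minor defect in the written definitions. As printed, MRT includes the mean input time and Vss includes CL times it. For a constant 3 h infusion under linear PK this is exactly 1.5 h and CL × 1.5 h. The percentages in step 2 rest further on one-compartment profiles and monkey half-lives and clearances; human values are not in the documents. Under saturable PK the direction held in all three fits at 0.3 to 1 mg/kg and the size is approximate.

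A reader might infer an effect on dose finding. There is none: no MTD, DLT or escalation rule uses MRT or Vss, both are reported descriptively, and both can be recomputed from retained data.

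**What to change.** In Protocol 8.5.3, and repeated in the SAP:

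- For MEN1309 and total antibody, define MRT = AUMC(0-∞)/AUC(0-∞) − mean input time, and Vss = CL × that MRT.
- Define mean input time as T/2 for an uninterrupted constant-rate infusion, and otherwise as the dose-weighted mean of the infusion-period midpoints, from the times and volumes recorded under 8.4.4.
- State that the correction is approximate if PK is non-linear.
- State that it does not apply to DM4 or S-methyl-DM4, which are not infused.
- As a secondary consistency change, compute AUMC by the same linear-log rule as AUC, after checking the printed AUMC line against the original protocol. On the scheduled times, subtracting 1.5 h then leaves 1.60 − 1.5 = 0.10 h (15 h half-life) and 1.55 − 1.5 = 0.05 h (31 h).

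The cost is wording in two documents and slightly more PK programming. Sampling and data collection do not change.

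### The accumulation ratio has no common time window, so it is biased when the last quantifiable PK sample differs between Cycle 1 and Cycle 2

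*Protocol*

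**What the plan says.** Protocol 8.5.3 defines AUC(0-t) as running "from time zero (pre-dose) to the time of the last quantifiable concentration", "calculated by means of the linear-log trapezoidal method". The upper limit t therefore belongs to the individual profile; it is neither a fixed time nor the dosing interval. Ro, the "Accumulation ratio following 2 consecutive infusions calculated as" a quotient, divides AUC(0-t) of the second infusion by AUC(0-t) of the first, using the same symbol.

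The samples that decide t are these:

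- At all dose levels, the intensive series ends with samples at "16, 24, 36, 48, and 72 hours after the end of the infusion of Cycle 1 and Cycle 2".
- In addition, "only for dose levels higher or equal to 0.8 mg/kg, PK blood samples will be taken at Visits 2 and 3 of each cycle", that is, on Day 8 and Day 15.
- At those dose levels, any extra safety sample between visits brings an extra PK sample (Protocol 2.4 and 8.5.3).

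The third rule in 8.5.3 for values below the LLOQ ends a profile at the first of two or more successive such values, separately within each dosing interval. Protocol 9.3.5 rules out imputation. SAP 5.1.1.5 lists AUC(0-t) and Ro by name only. The pharmacokinetics text in SAP 6.1.1.2 gives summary statistics but no window.

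**The concern.** A ratio of two areas measures accumulation only if both areas cover the same stretch of time. Here each area is cut where its own data happen to end. If one profile is shorter, the missing tail enters Ro as if exposure had changed between infusions. A short Cycle 2 profile looks like falling exposure, and a short Cycle 1 profile looks like accumulation.

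The PK profile after single and repeated doses is a secondary objective (Protocol 7.2), and Ro is the listed parameter that directly compares the two infusions. The monkey data in Protocol 6.2.2.3.1 suggest full clearance within three weeks. True accumulation may therefore be close to nil, and an artefact of 10 to 20% could exceed any real effect. Accelerated-titration cohorts hold one patient, so there one lost sample sets the cohort's value.

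Unequal profiles are foreseeable. Cycle 1 requires hospital stay through the 48 h procedures. From Cycle 2 the stay is not mandatory for patients whose Cycle 1 administration was uneventful (Protocol 8.5.1). Late samples may then be easier to lose in Cycle 2, although the documents give no rates.

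**Working it through.** The documents state no value for Ro, so there is no figure to reproduce. The check asks what the written formula returns when the true ratio is known.

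**Inputs from the protocol.** Infusion length T = 3 h (8.4.4). Dosing interval 21 days = 504 h (8.5.1). Last intensive samples at 48 h and 72 h after the end of infusion, that is, 51 h and 75 h from the start. Day 8 and Day 15 taken as 168 h and 336 h. Half-life 15 to 31 h, from single doses in monkeys (6.2.2.2).

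**Assumptions.** A linear one-compartment model with identical kinetics in both cycles. LLOQ taken as 0, and alternatively as 0.5% of dose/V.

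**True value.** The carry-over after 504 h is 2^(-504/31), about 0.00001, at the longer half-life. True Ro is therefore 1.00 at both half-lives.

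**Formula.** With k = ln 2 / half-life, the share of the total AUC reached by time t (t > T) is

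F(t) = 1 − [exp(−k(t − T)) − exp(−kt)] / (kT).

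With negligible carry-over, Ro as defined equals F(t in Cycle 2) / F(t in Cycle 1).

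| Half-life | F(51) | F(75) | F(168) | F(336) |
|---|---|---|---|---|
| 15 h | 0.8984 | 0.9665 | 0.9995 | 1.0000 |
| 31 h | 0.6693 | 0.8066 | 0.9758 | 0.9994 |

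**Matched windows.** Any t over the same t gives 1.00. The formula is sound when the last samples match.

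**Below 0.8 mg/kg, 72 h sample lost in one cycle:**

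- Cycle 2 only: 0.8984/0.9665 = 0.93 (15 h); 0.6693/0.8066 = 0.83 (31 h).
- Cycle 1 only: 0.9665/0.8984 = 1.08 (15 h); 0.8066/0.6693 = 1.205 (31 h).

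**At 0.8 mg/kg and above, Cycle 2 profile ending at 72 h:**

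- LLOQ 0, Cycle 1 running to Day 15: 0.9665/1.0000 = 0.97 (15 h); 0.8066/0.9994 = 0.81 (31 h).
- LLOQ 0.5% of dose/V: at 15 h the Day 8 level is about 0.05% of dose/V, so Cycle 1 also ends at 72 h and Ro = 1.00. At 31 h the Day 8 level is about 2.4% and the Day 15 level about 0.06%, so Cycle 1 ends on Day 8 and Ro = 0.8066/0.9758 = 0.83.
- Day 15 alone lost in Cycle 2, LLOQ 0: 1.00 (15 h) and 0.9758/0.9994 = 0.98 (31 h). With the higher LLOQ there is no effect.

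The linear-log trapezoid applied to the protocol's sampling times gives the same values to two decimals.

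**Effect on a cohort mean.** One patient at 0.83 and the rest at 1.00 gives 0.83 in a cohort of one, (2 + 0.83)/3 = 0.94 in a cohort of three, and (5 + 0.83)/6 = 0.97 in a cohort of six.

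**After the fix.** Cutting both areas at the shorter of the two last times returns Ro to 1.00 in every scenario above.

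**The case against.** The strongest reply is that the design itself creates no mismatch. The 72 h sample is scheduled in both cycles, and so are Day 8 and Day 15 at 0.8 mg/kg and above. This stands: the bias needs a last quantifiable sample that is lost, below the LLOQ or added in one cycle only.

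A reader might infer three stronger things that the documents do not support.

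- *Optional Cycle 2 sampling makes the windows unequal.* It is true that "PK blood sampling at 10, 12 and 16 hours after the end of infusion is informative but not mandatory" in Cycle 2, but these are interior points. The required 24, 36, 48 and 72 h samples follow them, so leaving them out does not move the last time, and in the model Ro is unchanged.
- *One missed Day 8 sample is enough.* It shortens the profile only if Day 15 is also missing or below the LLOQ; otherwise Day 8 is an interior point. Below 0.8 mg/kg no Day 8 sample is taken.
- *Dose decisions are affected.* The Cohort Review Committee sees PK data before escalation, but no DLT, MTD or escalation rule uses Ro.

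There are also partial safeguards. The PK population requires reliable assay data relevant to the parameter of interest, which could let a truncated profile be left out. The last quantifiable time, AUC(0-∞) and the extrapolated percentage are reported for both infusions, so a mismatch can be seen and repeat-dose exposure does not rest on Ro alone. These help a careful reader, but they do not change the formula or say when Ro should be withheld.

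**Conclusion.** The point holds in conditional form. As written, Ro is right when both profiles end at the same sampling time and biased when they do not, and nothing in either document prevents the second case. In the illustration the error ranges from nil to about 20%. It is negligible where the lost tail is already near zero or below the LLOQ, and it can go in either direction.

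These sizes rest on a linear model, on monkey half-lives at 3 and 5 mg/kg and on assumed LLOQs. The protocol calls the monkey kinetics non-linear and gives no human half-life or LLOQ, so the figures show scale and are not a forecast. Ro is descriptive and secondary, so this is a worthwhile clarification with no bearing on the primary endpoints.

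**What to change.** In Protocol 8.5.3 and SAP 5.1.1.5, define Ro over the same interval in both cycles of a patient. Use AUC over the 21-day dosing interval where it can be reliably estimated in both cycles; otherwise use the partial AUC to the latest time quantifiable in both. The SAP should state what counts as reliably estimable and when Ro is not calculated. The listing should show the common end time beside each Ro.

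The cost is a sentence or two and a partial-AUC setting; no new samples are needed. The downside is small: a shorter common window discards some late data, and if human kinetics are non-linear a ratio over a short window need not equal the ratio over the full interval. Showing the end time makes that limit visible.
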